The study is a prospective cohort study comprised of participants between ages 25-75 presenting to Atlanticare Regional Medical Center interventional pain department and Philadelphia College of Osteopathic Medicine OMM Clinic between April 2021 and May 2021 with trigger point in the upper trapezius muscle. It is expected that approximately 60 patients will be enrolled to produce approximately 50 evaluable subjects.

Inclusion Criteria: The subjects will only be recruited into the study if they have met all the following criteria:

- Ages between 25 and 60 years.
- Previous or current diagnosis of MTrP in the upper trapezius region according to the criteria set by Simons et al.³
- 1 active/latent MTrP in the upper trapezius region

The diagnostic criteria to establish myofascial trigger point is adopted from Travell and Simons³ and include:

1. Presence of palpable taut band in the skeletal muscle
2. Presence of hypersensitive tender spot in the taut band
3. Presence of local twitch response upon stimulation of the taut band
4. Reproduction of referred pain upon palpation
5. Presence of spontaneous referred pain pattern

Exclusion criteria: Any subject that exhibits any of the following criteria will be excluded from the study:

- Pregnancy or immunocompromise
- Fever/infection
- Previous history of whiplash injury
- Previous history of cervical surgery, cervical radiculopathy, or myelopathy
- Severe disc or cervical lesion
- Evidence of cognitive deficit
- Degenerative or inflammatory disease of the cervical spine or shoulder, fibromyalgia, or neuromuscular diseases
- Use of medications (anticoagulants, anti-inflammatory etc.) or illicit drug use (1 week prior to treatment or follow up)
- Received treatment for MPS a month before the study recruitment

All the patients of interest that present to AtlantiCare Regional Medical Center pain clinic and Philadelphia College of Osteopathic Medicine OMM Clinic that meet the relevant inclusion and exclusion criteria will be invited to participate in this study. The subjects will be informed of the purpose of the study and asked for informed consent. If recruited into the study, they will be administered a pre-intervention survey. Subjects will then be managed according to standard of care by their point of care physician. Following the intervention they will be administered a post-intervention survey immediately following the intervention and one-week post.

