Group 2 will be comprised of patients from AtlantiCare Regional Medical Center pain clinic and will be administered trigger point dry needling and lidocaine injection. The treatment will be administered by the pain clinic attending physician. After application of a coolant to numb the area, the isolated trigger point will be penetrated using a 30-gauge needle, to a depth adjusted depending on the patient, into the subcutaneous tissue. The patient will be warned about possible unpleasant sensations and mild pain associated with contraction of the tight band of muscle. Multiple needle insertions will be attempted to achieve MTrP inactivation, with the needle being withdrawn to the subcutaneous layer but not from the skin during each insertion, approximately lasting for 1-2 minutes ^{26,27}. Once the fascial tension is relieved, 0.5% lidocaine will be injected, and the needle will be withdrawn from the skin. The procedure will be terminated with hemostasis achieved.

Once the intervention is completed, the patient will be asked about the reduction in pain following the intervention and administered the post intervention survey. A week after the intervention, they will be called/mailed to ask about their pain intensity using the same post intervention survey by the medical students.

Safety Management:

Patients are free to withdraw from the study at any time should they choose to. Since the study procedures are not greater than minimal risk, adverse events are not expected. If any serious adverse effects or unaccounted events may occur, they will be reported to the IRB and patients will be discontinued from the study. The data from withdrawn patients will not contribute to the study statistics.

Data Analysis

The data will be analyzed using SPSS version 27.0 for Windows (IBM Corp. Released 2020. IBM SPSS Statistics for Windows, Version 27.0. Armonk, NY: IBM Corp). Values of interest include measures of central tendency, i.e. mean, standard deviation, normal distribution, confidence intervals etc. To be considered a statistically significant finding, the alpha level will be set at 0.05. A descriptive analyses of the outcome variables will be conducted to compare between the intervention groups. The homogeneity of sociodemographic data (age, sex, comorbid conditions) and treatment groups will be analyzed using the Fischer test and Pearson chi square test, respectively.

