Participants presenting to the Atlanticare Pain Management clinic received a lidocaine injection after dry needling into the location of the MTP by a board-certified pain management physician. First, the upper trapezius MTP was identified and isolated. After application of a coolant to numb the area, the isolated trigger point was penetrated using a 30-gauge needle, to a depth adjusted depending on the patient, into the subcutaneous tissue. The duration of treatment was approximately 1-2 minutes. Once the myofascial tension was relieved, 2 mL of 0.5% lidocaine was injected into the MTP.

After their respective interventions, the patient completed an immediate post-intervention survey, consisting of a 0-10 pain scale. Finally, approximately 7-10 days after the intervention, patients were contacted by telephone to complete the one-week post-intervention survey consisting of a 0-10 pain scale.

Outcome Measures

Pain intensity; measured using a point system; where 0 = no pain and 10 = maximum pain. Although this is a subjective measurement by the patient, we are interested in looking at the difference between pre- and post-intervention pain intensity ratings.

Data Analysis

The data was analyzed using R software. Values of interest include mean, median, standard deviation, normal distribution, confidence intervals etc. Intergroup and intra-group comparisons were conducted using independent t-tests and paired t-tests, respectively. Alpha level is set at 0.05 and p values less than that will be considered statistically significant. A descriptive analysis of the outcome variables was conducted to compare between the intervention groups. The homogeneity of sociodemographic data (age, sex, comorbid conditions) and outcome measures were analyzed using the Fischer test and Pearson chi square test, respectively.

The outcome measures were analyzed separately in both treatment groups. The contrast between the treatment groups was analyzed. A univariate analysis of the difference of the outcome variables at the different time points (before the intervention, immediately after the intervention, and a week post the intervention) were obtained through the student *t*-tests. A multivariate analysis was carried out using multiple logistic regression models with age, sex, and intervention group (Injection = 0, OMM = 1) factored as the independent variables.

Results

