The study was completed at two primary locations. There were a total of 10 eligible participants from the lidocaine treatment group and 21 eligible participants from the OMM treatment group enrolled after screening for the inclusion and exclusion criteria. 1 subject from the lidocaine treatment group was lost during follow-up at one week post intervention and thus excluded from the per protocol analysis of the study. The remaining participants' data were analyzed in SPSS 26. No significant difference was found between the two groups in regard to sociodemographic data (Table 1). At baseline, the OMM group had a mean pain intensity level of 2.76 (SD 1.8) while the lidocaine treatment group had a mean pain intensity level of 7 (SD 2.8). Descriptive statistics of pain intensity between the two groups demonstrate considerable variance (Table 2).

Within the OMM group, an independent samples t-test found a statistically significant difference between the pre-intervention and immediate post-intervention pain levels, $t(20) = 2.10, p = .048$. The mean pre-intervention pain level ($M = 2.76, SD = 1.84$) was significantly higher than the immediate post intervention pain level ($M = 1.86, SD = 0.96$). An independent samples t-test found a statistically significant difference between pre-intervention and one-week post-intervention pain levels, $t(20) = 2.68 p = .014$. The mean pre-intervention level of pain ($M = 2.76, SD = 1.84$) was significantly higher than one-week post-intervention ($M = 1.81, SD = 2.01$).

Within the lidocaine group, an independent samples t-test did not demonstrate a statistically significant difference between pre-intervention and immediate post-intervention pain levels, $t(20) = 1.17, p = 0.27$. The mean pain level pre-intervention ($M = 7, SD = 2.87$) was higher than immediately post-intervention ($M = 6.60, SD = 2.32$). When evaluating the difference in level of pain from pre-intervention to one-week post-intervention, an independent samples t-test was not statistically significant, $t(20) = 2.16 p = .062$. The mean level of pain pre-intervention ($M = 7, SD = 2.87$) was higher than one-week post-intervention ($M = 4, SD = 2.18$). Pain intensity between the two groups are also demonstrated graphically in Figure 1, with time point one corresponding to pre-intervention, two corresponding to immediately post-intervention and three corresponding to 1 week post intervention.

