To investigate the treatment effect between groups across time, a mixed design two factor ANOVA was utilized. As expected, due to small sample size, heterogeneity of covariance matrices was detected. This is considered a limitation of the study. Also, since a repeated measures design was implemented across three time periods, Mauchly's test of sphericity was examined and found to be significant ($p = .042$). This indicates that sphericity cannot be assumed, so a Greenhouse-Geisser statistic was computed. A statistically significant interaction effect was detected, $F(1.65, 56) = 3.90, p = .034$. Due to p-value being less than 0.05, we can confidently reject the null hypothesis and accept the alternative hypothesis.

[figure not shown]
Table 1.

Sociodemographic Data	Mean (SD) or Number (%)		P value
	OMM (n = 21)	Lidocaine (n = 10)	
Sex (%), n = 31 (100%)	21 (100)	10 (100)	
Male, n = 7 (22.6%)	5 (23.8)	2 (20)	
Female, n = 24 (77.4%)	16 (76.2)	8 (80)	
Age, y			
Subjects from 20 – 29 y, n = 22 (71%)	21 (100)	1 (10)	
Subjects from 30 – 39 y, n = 1 (3.2%)	0	1 (10)	
Subjects > 60y, n = 8 (25.8%)	0	8 (80)	
Ethnicity			
Caucasian, n = 20 (64.5%)	11 (52.4)	9 (90)	
African American, n = 1 (3.2%)	1 (4.8)	0	
Latino or Hispanic, n = 4 (12.9%)	3 (14.3)	1 (10)	
Asian, n = 6 (19.4%)	6 (28.6)	0	
Pain Intensity			
Pre-intervention	2.76 (1.8)	7 (2.8)	
Post-intervention (immediate)	1.86 (0.9)	6.6 (2.3)	0.026
Post-intervention (one week)	1.81 (2.0)	4 (2.2)	0.062

Table 2.

	Group	Mean	Std. Deviation	N
Pre-intervention Pain	OMM	2.76	1.84	21
	Lidocaine	7.00	3.04	9
	Total	4.03	2.96	30
Post-intervention immediate pain	OMM	1.86	0.96	21
	Lidocaine	6.56	2.45	9
	Total	3.27	2.66	30
Post-intervention 1 week pain	OMM	1.81	2.01	21
	Lidocaine	4.00	2.17	9
	Total	2.47	2.27	30

Figure 1.

Discussion

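### Significance tests cannot show that the two clinic-allocated groups are comparable at 21 v 10, and the SAP's statement of no sociodemographic difference conflicts with its own age data and has no comorbidity figures behind it

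*Protocol*

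**What the plan says.** Group membership is set by site: the Protocol (Intervention) and the SAP (Study Design) give muscle energy treatment at the osteopathic clinic and lidocaine with needling at the pain clinic. There is no randomisation.

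On comparability the Protocol's Data Analysis states: "The homogeneity of sociodemographic data (age, sex, comorbid conditions) and treatment groups will be analyzed using the Fischer test"; Pearson's chi-square is assigned to the second item, the treatment groups. The SAP's Data Analysis has: "The homogeneity of sociodemographic data (age, sex, comorbid conditions) and outcome measures were analyzed using the Fischer test and Pearson chi square test, respectively". That second item differs between the documents, but both assign Fisher's test to the sociodemographic variables and both name comorbid conditions. The threshold is in the Protocol: "To be considered a statistically significant finding, the alpha level will be set at 0.05"; the SAP uses the same level.

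The Protocol's Study Design expected that "approximately 60 patients will be enrolled to produce approximately 50 evaluable subjects", with no split by group. The SAP's Results report "10 eligible participants from the lidocaine treatment group and 21 eligible participants from the OMM treatment group". They then say, citing Table 1, that the groups did not differ significantly in sociodemographic data. Table 1 has rows for sex, age band, ethnicity and pain. It has none for comorbid conditions, and no other part of the SAP gives them.

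**The concern.** A homogeneity test asks whether an imbalance could be chance. In a comparison allocated by clinic the useful question is how large the imbalance is in the patients actually compared, because that is what can bias the treatment contrast. With ten patients in one group, a test at 0.05 can miss differences large enough to matter, and a non-significant result then reads as reassurance.

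What is at stake is the comparability statement behind the SAP's Conclusion that the two treatments have similar value, and behind its Discussion, which speaks of non-inferiority. If the groups are unlike in age, ethnicity, baseline pain and possibly comorbidity, a reader needs to see that next to the result. A reader who meets only the Results sentence would take the sociodemographic question as settled.

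**Working it through.** **Inputs.** Group sizes 21 (OMM) and 10 (lidocaine), from the SAP's Results. Counts from SAP Table 1, OMM v lidocaine: male 5/21 v 2/10; age 20–29 21/21 v 1/10, 30–39 0/21 v 1/10, over 60 0/21 v 8/10; Caucasian 11/21 v 9/10; African American 1/21 v 0/10; Latino or Hispanic 3/21 v 1/10; Asian 6/21 v 0/10. Baseline pain 2.76 (SD 1.8) v 7 (SD 2.8). Alpha is 0.05; two-sided is assumed because sidedness is not stated.

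**1. Does the SAP's statement reproduce?** Fisher's exact test (Freeman–Halton for more than two categories) and uncorrected Pearson chi-square:

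| Variable | Fisher / exact p | Pearson p |
|---|---|---|
| Sex | 1.00 | 0.81 |
| Ethnicity, 4 categories | 0.147 | 0.178 |
| Caucasian v other | 0.055 | 0.041 |
| Asian v other | 0.141 | 0.060 |
| Age, 3 bands | 5.0e-7 | 1.6e-6 |
| Age over 60 v not | 5.7e-6 | 2.0e-6 |

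The statement reproduces for sex and for four-category ethnicity. For Caucasian v other it depends on the test. For age it fails on every version tried.

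**2. How large are the imbalances?** For proportions, d = (p2 − p1) / √{[p1(1 − p1) + p2(1 − p2)] / 2}; absolute values are given.

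- Caucasian: (0.900 − 0.524) / √[(0.249 + 0.090)/2] = 0.376 / 0.412 = 0.91
- Asian: 0.286 / √[(0.204 + 0)/2] = 0.286 / 0.319 = 0.89
- Over 60: 0.800 / √[(0 + 0.160)/2] = 0.800 / 0.283 = 2.83
- Male: 0.038 / √[(0.181 + 0.160)/2] = 0.038 / 0.413 = 0.09
- Baseline pain: (7 − 2.76) / √[(1.8² + 2.8²)/2] = 4.24 / 2.354 = 1.80

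Sex is close. Both ethnicity contrasts are around 0.9, whichever side of 0.05 the p value falls.

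**3. Power of Fisher's test.** Power is the summed binomial probability of every table with two-sided Fisher p < 0.05. The rates are assumed, since the documents give none for comorbidity.

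| Assumed rates (n = 21 v n = 10) | Power |
|---|---|
| 10% v 30% | 21% |
| 20% v 40% | 16% |
| 20% v 50% | 32% |
| 50% v 80% | 26% |
| 10% v 50% | 61% |
| 5% v 80% | 99.5% |

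If the roughly 50 evaluable patients in the Protocol had split 25 v 25 (an assumption), 20% v 50% would still have only 51% power.

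**4. The SAP against itself.** The Results deny a significant sociodemographic difference. Table 1 shows every OMM patient in their twenties and eight of ten lidocaine patients over 60. The Discussion lists a substantial age difference, and a significantly lower baseline pain in the OMM group, as limitations. These three places cannot all stand.

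**5. Comorbid conditions.** They are named in both Data Analysis sections and have no figures anywhere, so nothing can be computed.

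**The case against.** The strongest reply has four parts.

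First, neither document attaches a decision to the homogeneity tests, and the SAP's Discussion openly says that age and baseline pain differ and that this hampered the comparison. That stands, and it rules out saying that the SAP as a whole presents the groups as alike. It does not repair the Results sentence, and the Discussion does not mention ethnicity or comorbidity.

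Second, a reader might infer that the tests are the plan's sole protection against confounding. The documents do not support that. The SAP also plans a regression with age, sex and intervention group, and both documents exclude several neck, inflammatory and neuromuscular conditions. The regression does not include ethnicity, comorbidity or baseline pain, and no results from it appear.

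Third, a reader might infer that low power explains the Results sentence, or that the tests would pass any imbalance. They would not. Fisher's test flags age beyond doubt, so the age statement is a contradiction in the reporting and would be wrong at any sample size.

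Fourth, ethnicity is not among the variables named in the testing rule, no ethnicity p value is visible in Table 1, and Pearson on Caucasian v other is below 0.05. Nothing in the documents shows that ethnicity affects pain response. All of this is right. Ethnicity serves here to show that imbalances of about 0.9 can pass or fail according to test and grouping. It does not establish a bias.

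Nor do the documents show that a comorbidity test was run and withheld. The Results sentence cites Table 1, which has no such row. The supported reading is that comparability on comorbidity is unknown.

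**Conclusion.** The point holds in this form. Judging comparability by significance tests is the wrong method for a 21 v 10 comparison allocated by clinic: power is roughly 16–61% for assumed differences of 20 to 40 percentage points, and observed ethnicity differences of 0.91 and 0.89 standardised units can pass as non-significant. Separately, the Results sentence is contradicted for age by Table 1 (0% v 80% over 60, standardised difference 2.83) and by the Discussion, and it cannot extend to comorbid conditions. Baseline pain differs by 4.24 points, about 1.8 SD, which the SAP concedes.

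The counts are the SAP's own. The power figures rest on assumed rates and two-sided testing, and the 25 v 25 figure on an assumed split. The direction and size of any resulting bias in the treatment comparison cannot be derived from the documents.

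**What to change.** In the SAP's Data Analysis, and in the matching Protocol sentence, replace the homogeneity tests with wording such as: *Comparability of the groups is described by counts (or means and SDs) and standardised differences for age, sex, ethnicity, comorbid conditions and baseline pain. No p values are used.*

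Set no pass/fail cut-off. At 21 v 10 the standard error of a standardised difference under no true difference is about √(1/21 + 1/10) = 0.38, so a threshold such as 0.25 would be exceeded about half the time by chance: 0.25/0.38 = 0.65, two-sided probability about 0.52. Sizes should be shown and discussed, not graded.

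Replace the Results sentence with a statement, consistent with the Discussion, that the groups differ markedly in age, ethnicity and baseline pain, so the between-group comparison is open to confounding.

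Add comorbidity by group to Table 1, or state that it was not collected and that comparability on it is unknown.

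Because results are already reported, record the change as a dated revision. The cost is wording and a re-run of Table 1 on data already held, plus a less favourable comparability statement. The change describes confounding; it does not remove it.
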